10.2 Prohibited Medications, Devices, Treatments and Procedures

1445

Participants are not permitted to initiate use of a blood glucose lowering medication that was not in use and met eligibility criteria at the time of screening. This includes but is not limited to SGLT2 inhibitor, sulfonylurea, GLP1, pramlintide, or metformin drugs.

1448

Participants are not permitted to use diabetes management devices that are not FDA approved (such as do-it-yourself closed-loop systems).

1450

10.3 Rescue Medications

1451

All participants will be required to have a commercially available glucagon (or glucagon analog) preparation for treatment as needed of severe hypoglycemia.

1453

10.4 Pregnancy Reporting

1454

If pregnancy occurs, the study intervention will be discontinued while continuing safety follow-up. The occurrence of pregnancy will be reported to the Coordinating Center and to the JCHR IRB on the Unanticipated Problem form within 7 calendar days of becoming aware of the pregnancy.

1458

10.5 Participant Compensation

1459

Participant compensation will be described in the informed consent form.

1460 **10.6 Participant Withdrawal**

1461 Participation in the study is voluntary, and a participant may withdraw at any time.

1462 For participants who withdraw, their data will be used up until the time of withdrawal.

1463 For participants using the BP who withdraw, a study provider will help them transition to their

1464 own CSII or MDI therapy safely.

1465 **10.7 Confidentiality**

1466 For security and confidentiality purposes, participants will be assigned identifiers that will be

1467 used instead of their names. Protected health information gathered for this study will be shared

1468 with the Coordinating Center, the Jaeb Center for Health Research in Tampa, FL. De-identified

1469 participant information may also be provided to research sites involved in the study.

1470

Chapter 11: Statistical Considerations

11.1 Statistical and Analytical Plans

1473 The approach to sample size and statistical analyses are summarized below. A detailed statistical
1474 analysis plan will be written and finalized prior to the start of the study.

11.2 Statistical Hypotheses

1476 The primary outcome is:

- Superiority in HbA1c at 13 weeks

1479 A key secondary outcome is

- Non-inferiority in CGM-measured time <54 mg/dL calculated over 13 weeks

Only superiority in HbA1c at 13 weeks needs to be met to declare efficacy. Primary outcome analyses will combine pediatric and adult participants into a single analysis. The study hypotheses can be stated as follows:

1484 HbA1c Outcome:

- *Null Hypothesis:* There is no difference in the mean HbA1c at 13 weeks between BP aspart/lispro and Control Group
- *Alternative Hypothesis:* There is a nonzero difference in the mean HbA1c at 13 weeks between BP aspart/lispro and Control Group

1489 Time <54 mg/dL Outcome:

- *Null Hypothesis:* There is a mean difference of at least 1% in the percentage of time spent with a sensor glucose level below 54 mg/dL between the BP aspart/lispro and Control Group over the 13 weeks
- *Alternative Hypothesis:* There is a mean difference of less than 1% in the percentage of time spent with a sensor glucose level below 54 mg/dL between the BP aspart/lispro and Control Group over the 13 weeks

1496 The primary analyses will include only the BP aspart/lispro Groups compared with the Control
1497 Group. Separate analyses will be performed comparing BP Fiasp and Control Groups as
1498 described in Section 11.12, but no multiplicity adjustment will be applied as these can be
1499 considered two separate studies for purpose of analysis.

11.3 Sample Size

1501 The sample size of 440 for the RCT was selected to provide sufficient exposure to the iLet BP
1502 system for regulatory purposes, with respect to different age groups and to use of both insulin
1503 aspart/lispro and Fiasp. RCT completion is expected for 200 participants randomized to BP
1504 aspart/lispro Group, 100 to the BP Fiasp Group, and 100 to the Control Group.

1505 The primary analysis for BP aspart/lispro vs. Control Group will include both the pediatric and
1506 adult participants in a single analysis. Superiority for HbA1c at 13 weeks and non-inferiority for
1507 time <54 mg/dL measured with CGM at intervals over the 13 weeks are considered primary
1508 endpoints. Statistical power for each endpoint was computed assuming the following:

1509 HbA1c: Statistical power is >99%, assuming true mean HbA1c difference of 0.4% between BP
1510 aspart/lispro and Control Group, standard deviation of 13-week HbA1c of 0.8%, correlation
1511 between baseline and 13-week HbA1c of 0.40, two-sided type 1 error of 5%
1512 Time <54 mg/dL: Statistical power is 99%, assuming no true difference in mean time <54 mg/dL
1513 between BP aspart/lispro and Control Group, a non-inferiority margin of 1%, standard deviation
1514 of percent time <54 mg/dL of 2.0%, correlation between baseline and follow-up of 0.40, and
1515 one-sided type 1 error of 0.025%
1516 Power calculations comparing BP Fiasp and Control Group are described in Section 11.12.

1517 **11.4 Efficacy Outcome Measures**

1518 **11.4.1 Primary and Key Secondary Efficacy Endpoints**

1519 HbA1c at 13 weeks (superiority)
1520 CGM time < 54 mg/dL (non-inferiority)

1521 To preserve the overall type 1 error, a hierarchical gatekeeping testing procedure will be used
1522 with HbA1c at 13 weeks tested first. If the HbA1c analysis results in a statistically significant
1523 result ($p < 0.05$), then testing will proceed to the CGM time <54 mg/dL analysis.

1524 **11.4.2 Additional Secondary Efficacy Endpoints**

1525 **11.4.2.1 Secondary Efficacy Endpoints Included in Hierarchical Analysis**

1526 Assuming the primary and key secondary endpoints meet statistical significance as described
1527 above, the following CGM-measured secondary endpoints will be tested for superiority in a
1528 hierarchical fashion as described in Section 11.6.4.

1529 Mean glucose
1530 Time 70-180 mg/dL
1531 Time >180 mg/dL
1532 Time >250 mg/dL
1533 Standard deviation
1534 Time <70 mg/dL
1535 Time <54 mg/dL
1536 Coefficient of variation

1537 **11.4.2.2 Other Secondary Efficacy Endpoints**

1538 The following endpoints are considered exploratory. Type 1 error for these endpoints will be
1539 controlled using the false discovery rate (FDR). The Fiasp and aspart/lispro groups will be
1540 pooled for analyses of the secondary efficacy endpoints listed in this section if there are not
1541 statistically significant differences comparing the Fiasp and aspart/lispro groups for the primary
1542 and key secondary outcomes, as described in section 11.14.

1543 **HbA1c:**

1544 HbA1c <7.0% at 13 weeks
1545 HbA1c <7.0% at 13 weeks in participants with baseline HbA1c >7.5%
1546 HbA1c <7.5% at 13 weeks
1547 HbA1c <8.0% at 13 weeks
1548 HbA1c >9.0% at 13 weeks
1549 HbA1c improvement from baseline to 13 weeks >0.5%
1550 HbA1c improvement from baseline to 13 weeks >1.0%
1551 HbA1c relative improvement from baseline to 13 weeks >10%
1552 HbA1c improvement from baseline to 13 weeks >1.0% or HbA1c <7.0% at 13 weeks

1553 CGM-Measured:

1554 Time in range 70-140 mg/dL
1555 Time in range 70-120 mg/dL
1556 Time <60 mg/dL
1557 Area over the curve (70 mg/dL)
1558 Low blood glucose index
1559 CGM-measured hypoglycemic events (\geq 15 minutes with glucose concentration <54 mg/dL)
1560 CGM-measured hyperglycemic events (\geq 15 minutes with glucose concentration >300 mg/dL)
1561 Time >300 mg/dL
1562 Area under the curve (180 mg/L)
1563 High blood glucose index
1564 Time in range 70-180 mg/dL >70%
1565 Time in range 70-180 mg/dL improvement from baseline to 13 weeks \geq 5%
1566 Time in range 70-180 mg/dL improvement from baseline to 13 weeks \geq 10%
1567 Mean of daily difference (MODD)
1568 Time <70 mg/dL <4%
1569 Time <54 mg/dL <1%

1572 Combined Secondary Outcomes:

1573 Improvement in HbA1c > 0.5% without an increase in time < 54 mg/dL by > 0.5% OR
1574 improvement in time < 54 mg/dL by > 0.5% without an increase in HbA1c by > 0.5%

1575 Improvement in time 70–180 mg/dl by >10% without an increase in time < 54 mg/dl by >
1576 0.5% OR improvement in time < 54 mg/dl by > 0.5% without a decrease in time 70–180
1577 mg/dl by > 10%
1578 $BGRI = LBGI + HBGI$
1579 Mean glucose <154 mg/dL and time <54 mg/dL <1%
1580 Time in range 70-180 mg/dL >70% and time <54 mg/dL <1%

1581 **Other Secondary Outcomes:**

1582 Questionnaires scores on each questionnaire that is administered (see chapter 8)
1583 Insulin

- 1584 ○ Total daily insulin (units/kg)
- 1585 ○ Percentage change in the TDD of insulin over the first two-week period relative to
1586 the TDD of insulin in last two-week period (iLet Group only)

1587 Weight and Body Mass Index (BMI)
1588 From the weekly questionnaires, number of hypoglycemic events requiring carbohydrate
1589 treatment per 24 hours
1590 From the weekly questionnaires, grams of carbohydrate taken specifically to treat
1591 hypoglycemic events per 24 hours

1592 **11.5 CGM Metrics Calculations**

1593 Baseline values for each CGM metric will be computed from either the participant's personal
1594 Dexcom G6 data or from the G6 wear prior to randomization. The most recent two weeks of
1595 CGM data prior to randomization will be included in the calculation of baseline CGM metrics.
1596 During the RCT, CGM metrics will be calculated from the CGM data collected from the Control
1597 Group for comparison with the CGM data from the BP Group. Percentage of CGM values that
1598 fall within a specified range will be calculated by dividing the number of CGM values that fall
1599 within the range by the total number of CGM readings.

1600 **11.6 Analysis of the Primary and Secondary Efficacy Endpoints**

1601 The primary analysis will include both the pediatric and adult participants in a single analysis.
1602 All analyses comparing the BP aspart/lispro with the Control Group will follow the intention-to-
1603 treat (ITT) principle with the data from each participant analyzed according to the treatment
1604 assigned by randomization.

1605 A per-protocol analysis that includes participants adhering to the protocol will be performed and
1606 detailed in the SAP. Sensitivity analyses on the primary and key secondary outcomes also will
1607 be described in the SAP.

1608 **11.6.1 HbA1c Analyses (Superiority)**

1609 HbA1c at 13 weeks will be compared between the BP aspart/lispro and Control Groups using a
1610 linear mixed effects regression model adjusting for baseline HbA1c, age, and clinical center

1611 (random factor). HbA1c is expected to be normally distributed, but regression diagnostics will
1612 be performed to check the residuals and an appropriate alternative transformation or a
1613 nonparametric analysis based on ranks will be performed if the residuals have a skewed
1614 distribution. In the event that some HbA1c values are not available at 13 weeks, then the linear
1615 mixed effect regression model will use the method of direct likelihood to incorporate information
1616 from baseline measurements to calculate the maximum likelihood at 13 weeks. Only central lab
1617 HbA1c measurements will be used in the analyses.

1618 Other secondary HbA1c outcomes will be tested and described in the SAP.

11.6.2 Time <54 mg/dL (Noninferiority)

1620 Time below 54 mg/dL will be calculated over 13 weeks for each subject as described in
1621 Section 11.5. A two-sided 95% confidence interval on the mean difference in % time <54 mg/dL
1622 between BP aspart/lispro and Control Group will be performed based on a linear mixed effects
1623 regression model adjusting for baseline % time <54 mg/dL, age, and clinical center (random
1624 factor). Noninferiority will be assessed by comparing the upper bound of this confidence
1625 interval to a noninferiority limit of 1%. Missing data will be handled by the method of direct
1626 likelihood. Residuals values will be examined for an approximate normal distribution. If the
1627 values are highly skewed, then a transformation or nonparametric method will be used instead.
1628 A two-sided p-value will be reported, and a 5% significance level will be used to declare
1629 significance.

1630 Since noninferiority is typically framed in terms of a one-sided test, it is worth noting that the left
1631 half of a two-sided test at alpha = 0.05 gives the same rejection region as a one-sided test at alpha
1632 = 0.025. Therefore, reporting a two-sided 95% confidence interval will provide flexibility to test
1633 for inferiority if noninferiority cannot be declared while maintaining the overall type 1 error rate
1634 of 5%.

11.6.3 Secondary CGM Metrics (Superiority)

1636 Summary statistics (mean \pm SD or median (quartiles)) will be reported for the CGM-measured
1637 metrics at baseline and during follow up as well as for differences from baseline by treatment
1638 group.

1639 Secondary CGM metrics will be calculated as described in Section 11.5. CGM metric
1640 differences between BP and Control Groups will be compared using a linear mixed effects
1641 regression model adjusting for the baseline value of the metric, age, and clinical center (random
1642 effect). Residual values will be examined for an approximate normal distribution. If residuals
1643 are highly skewed, then a transformation or robust statistical method (e.g., non-parametric or
1644 MM estimation) will be used instead. Missing data will be handled using direct likelihood.

11.6.4 Hierarchical Analyses

1646 To preserve the overall type 1 error for the primary endpoint and key secondary endpoint as
1647 defined in section 11.4.1 and selected secondary endpoints listed in section 11.4.2.1, a
1648 hierarchical testing procedure will be used. If the primary analysis for HbA1c results in a
1649 statistically significant result ($p < 0.05$), then testing at the 0.05 level will proceed to the next
1650 outcome metric. This process continues iteratively moving to the next variable down on the list
1651 until a non-significant result is observed, or all 10 variables have been tested. If a non-

1652 significant result is encountered, then formal statistical hypothesis testing is terminated and any
1653 variables lower on the list will not be formally tested.

1654 Regardless of the results of the hierarchical testing, summary statistics appropriate to the
1655 distribution will be tabulated by treatment group for each hierarchical outcome. A 95%
1656 confidence interval for the treatment group difference also will be calculated for all hierarchical
1657 outcomes listed above. However, a confidence interval that excludes zero will not be considered
1658 a statistically significant result if an outcome variable higher on the hierarchical list failed to
1659 reach statistical significance.

1660 **11.6.5 Questionnaires and Other Outcomes Analyses**

1661 For questionnaires administered to both randomization groups, comparisons will be made using
1662 similar linear models as described above for the primary and key secondary outcomes. If
1663 questionnaires include a total score, separate models will be run for the total score and any
1664 subscales listed in section 8.2.2.

1665 Similarly, for insulin, weight and BMI metrics comparisons will be made using similar linear
1666 models as described above for the primary HbA1c analysis.

1667 Details of the questionnaire scoring and other outcome assessment will be detailed in the SAP.

1668 **11.7 Safety Analyses**

1669 All randomized participants will be included in the safety analyses and all of their post-
1670 randomization safety events will be reported. Separately, any adverse events occurring between
1671 screening and randomization will be reported.

1672 All reportable adverse events will be tabulated by treatment group (aspart/lispro and Fiasp
1673 groups will be reported separately). Details will be provided in a listing of each event, including
1674 Medical Dictionary for Regulatory Activities (MedDRA) term and MedDRA System Organ
1675 Class. Safety analyses for the RCT will include events occurring on or after randomization until
1676 and including the 13-week visit or Day 98 from randomization, whichever occurs first.

1677 Formal statistical testing only will be performed for selected safety endpoints. For the following
1678 outcomes, mean \pm SD or summary statistics appropriate to the distribution will be tabulated by
1679 treatment group and formal statistical comparisons will be performed if there are enough events
1680 (at least 5 events combined between the BP aspart/lispro and Control Group):

1681 Number of SH events and SH event rate per 100 person-years

1682 Number of DKA events and DKA event rate per 100 person-years

1683 Other serious adverse events

1684 Worsening of HbA1c from baseline to 13 weeks by >0.5%

1685 If enough events occur for the severe hypoglycemia and DKA outcomes and other serious
1686 adverse events, the numbers of events will be compared between the two treatment groups
1687 during the RCT using a robust Poisson regression as detailed in the SAP.

1688 Since the Control Group is not provided with a study blood glucose meter or blood ketone meter,
1689 no treatment group comparisons of meter data will be performed. Additionally, no formal
1690 statistical comparison will be made of all reported adverse events combined since there are

1691 specific requirements in the protocol for reporting certain events in real-time for the BP Group
1692 but not the Control Group, and adverse device effects are only reported for the BP Group.

11.7.1 Safety Tabulations Specific to the BP Group

1694 For the BP Group, all of the following will be tabulated separately for the BP aspart/lispro Group
1695 and the Fiasp Group:

1696 Adverse device effects (ADE)

1697 Serious adverse device events (SADE)

1698 Unanticipated adverse device effects (UADE)

11.8 Additional Tabulations and Analyses

1700 The following tabulations will be performed according to treatment group:

1701 Baseline demographics and clinical characteristics

1702 A flow chart accounting for all participants for all visits

1703 Visit completion rates for each follow-up visit

1704 Protocol deviations

1705 Modifications in diabetes management class in the Control Group (e.g. change between
1706 MDI/CSII) during the study

1707 Number and reasons for unscheduled visits and phone calls

11.8.1 Tabulations Specific to the BP Group

1709 Number of participants who stopped BP use and reasons

1710 % time in closed loop

1711 Occlusion events that occur while using the iLet BP system

1712 Device malfunctions requiring study team contact and other reported device issues

11.9 Planned Interim Analyses

1714 No formal interim efficacy analyses are planned as study recruitment is expected to be rapid and
1715 the duration of follow up short. The DSMB will review safety data at intervals, with no formal
1716 stopping rules other than the guidelines provided in the participant-level and study-level stopping
1717 criteria (as defined in Section 9.6 of the protocol).

1718

1719 Upon completion of the RCT, the efficacy and safety analyses will be performed in preparation
1720 for PMA submission.

11.10 Subgroup Analyses

1722 In exploratory analyses, the primary and key secondary outcomes plus time in range 70-180
1723 mg/dL and mean glucose will be assessed separately for interaction with certain baseline
1724 variables, including baseline HbA1c, prior pump/CGM use, and other baseline characteristics as

1725 described in the SAP. The Fiasp and aspart/lispro Groups will be pooled if there are not
1726 statistically significant differences comparing the Fiasp and aspart/lispro Groups for the primary
1727 endpoints as described in section 11.14, with the exception of subgroup analyses by age, in
1728 which only the BP aspart/lispro group will be compared with the Control Group. All primary and
1729 key secondary variables will be evaluated in the predefined age groups (≥ 18 years old and < 18
1730 years old, and further subdivided as 6- < 13 , 13- < 18 , 18- < 26 , 26- < 50 , ≥ 50 years
1731 old). Interpretation of the subgroup analyses will be made with caution, particularly if the primary
1732 analysis is not significant.

1733 **11.11 Multiple Comparison/Multiplicity**

1734 Hierarchical Analyses

1735 The hierarchical testing procedure described above in Section 11.6.1 will be used to control the
1736 overall type 1 error for the primary endpoint and key secondary endpoints plus eight additional
1737 secondary outcomes identified above.

1738 All Other Secondary Analyses

1739 For the other secondary analyses, the false discovery rate will be controlled using the adaptive
1740 Benjamini-Hochberg procedure.

1741 **11.12 Additional Exploratory Analyses**

1742 Additional analyses comparing treatment groups will include:

1743 Comparison of aspart/lispro BP Group versus Control Group in adults ≥ 18 years old for
1744 the efficacy and safety outcomes described for the main RCT analyses

1745 Separate CGM analyses for daytime and nighttime

1746 Total daily dose of insulin at 13 weeks and at 2 weeks according to baseline HbA1c

1747 Intersubject variability of HbA1c

1748 **11.13 BP Fiasp Versus Control Group**

1749 All of the above analyses with the exception of subgroup analyses by age group will be
1750 replicated comparing the BP Fiasp and Control Groups. This analysis will be treated as a
1751 separate study, so the multiple hypothesis testing in the BP aspart/lispro vs Control comparison
1752 will not be adjusted for the BP Fiasp vs. Control Group comparison. However, the same
1753 hierarchical testing procedure will be performed for the BP Fiasp versus Control comparison for
1754 primary and secondary endpoints and the false discovery rate will be controlled for the other
1755 secondary endpoints as described in Section 11.11.

1756 This analysis will include approximately 100 participants in BP Fiasp and 50 participants in
1757 Control Group. Statistical power for each primary endpoint was computed assuming the
1758 following:

1759 HbA1c: Statistical power is 91%, assuming true mean HbA1c difference of 0.4% between BP
1760 Fiasp and Control Group, standard deviation of 13-week HbA1c of 0.8%, correlation between
1761 baseline and 13-week HbA1c of 0.40, two-sided type 1 error of 5%

1762 Time <54 mg/dL: Statistical power is 86%, assuming no true difference in mean time <54 mg/dL
1763 between BP Fiasp and Control Group, a non-inferiority margin of 1%, standard deviation of
1764 percent time <54 mg/dL of 2.0%, correlation between baseline and follow-up of 0.40, and one-
1765 sided type 1 error of 0.025%

1766 **11.14 Comparison of Aspart/Lispro Group and Fiasp Group**

1767 For the primary and key secondary endpoints, the BP aspart/lispro Group and the BP Fiasp
1768 Group will be compared. If neither analysis has a p value >0.05 for superiority, then these
1769 groups will be pooled for the exploratory secondary and subgroup analyses that are not part of
1770 the hierarchy analyses.

1771 **11.15 Transition Phase**

1772 In the 2-4-day Transition Phase, participants are randomly assigned to transition back to their
1773 usual therapy based on therapeutic guidance from the bionic pancreas or transition back to their
1774 usual therapy based on their own insulin regimens prior to enrolling in the RCT.

1775 Analyses will be considered exploratory. The primary analyses will be for safety, tabulating
1776 events. Exploratory analyses will include mean CGM glucose level and time of CGM measured
1777 time < 54 mg/dL.

1778

Chapter 12: Data Collection and Monitoring

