Treatment Groups	
Pediatric (6-<18 years old) RCT Period: Random assignment in a 2:1 ratio to the BP Group (with lispro or aspart) or the Control Group (~110 and ~55 participants, respectively) for a period of 13 weeks, such that a minimum of 100 in the BP Group will complete the 13-week RCT.
 
Adult (\geq18 years) RCT Period: Random assignment in a 2:2:1 ratio to the BP Group (with lispro or aspart), the BP Fiasp Group, or the Control Group (~110, 110, and 55 participants, respectively) for a period of 13 weeks such that a minimum of 100 in each BP Group complete the 13-week RCT.
 
Transition Phase (all adult and pediatric participants at end of RCT [BP Group]): random assignment in a 1:1 ratio to transition back to either participant's usual therapy or the dosing recommendations from the iLet BP.

Participant Duration	~3 months

Description	
Protocol Overview/Synopsis	
The study has two major parts: (1) the RCT Period, and (2) the Transition Phase. These parts are described below and detailed in the main part of the protocol.
 
The 13-week, parallel-group, multi-center RCT Period is designed to compare the insulin-only iLet BP Group using insulin lispro, insulin aspart, or Fiasp (adults only); and a control group using CGM (Control Group). Upon completion of the RCT Period, the BP Group will enter the 2–4 day Transition Phase and eligible participants in the Control Group will be offered participation in a separate Extension Study.
 
A 2–4 day Transition Phase will be conducted for all participants who complete BP use at the end of the RCT Period (BP Group). Participants will be randomly assigned (1:1) to either transition back to their usual mode of therapy (MDI or pump therapy) based on therapeutic guidance from the iLet BP system or transition back to their usual mode of therapy based on what their own insulin regimens were prior to enrolling in the RCT Period. For those randomized to using their pre-study regimens, the dosing can be adjusted by the investigator to mitigate safety issues but should follow pre-study regimen as closely as possible.

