## 52 **5. Sample Size**

53 The sample size of 440 for the RCT was selected to provide sufficient exposure to the iLet BP  
54 system for regulatory purposes, with respect to different age groups and for use of both insulin  
55 aspart/lispro and Fiasp. RCT completion is expected for 100 adults randomized to the BP Fiasp  
56 group, 100 adults randomized to BP aspart/lispro Group, and 50 adults randomized to the  
57 Control Group.

58

59 Superiority for HbA1c at 13 weeks and non-inferiority for time <54 mg/dL measured with  
60 CGM at intervals over the 13 weeks are considered the primary and key secondary endpoints,  
61 respectively. Statistical power for each endpoint was computed assuming the following:

62

63     • HbA1c: Statistical power is 91%, assuming true mean HbA1c difference of 0.4% between  
64         BP Fiasp and Control Group, standard deviation of 13-week HbA1c of 0.8%, correlation  
65         between baseline and 13-week HbA1c of 0.40, two-sided type 1 error of 5%

66     • Time <54 mg/dL: Statistical power is 86%, assuming no true difference in mean time <54  
67         mg/dL between BP Fiasp and Control Group, a non-inferiority margin of 1%, standard  
68         deviation of percent time <54 mg/dL of 2.0%, correlation between baseline and follow-up of  
69         0.40, and one-sided type 1 error of 0.025%

70

71 A separate document details the justification of these power calculations.

72

73 **6. Analysis of Efficacy and Safety Endpoints**

74 All efficacy analyses (including exploratory analyses and tabulation-only analyses) and safety  
75 analyses comparing the BP Fiasp vs. Control group will be the same as described in the BP  
76 aspart/lispro vs Control Group SAP detailed separately in the Appendix, with the following  
77 difference:

78 • All analyses comparing BP Fiasp vs. Control are restricted to adults only

79 **80 7. Comparison of the BP Fiasp vs. BP aspart/lispro Groups**

81 All efficacy analyses (including exploratory analyses and tabulation-only analyses) and safety  
82 analyses comparing the BP Fiasp vs. BP aspart/lispro group will be the same as described in the  
83 BP Aspart/lispro vs Control Group SAP detailed separately in the Appendix, with the following  
84 differences:

85 • All analyses comparing BP Fiasp vs. BP aspart/lispro are restricted to adults only  
86 • The study was not formally powered for these analyses, so primary and hierarchical  

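### The two Fiasp-versus-Control powers (91% and 86%) rest on the same standardised inputs, which give about 88% for both; the one-sided alpha is also misprinted as 0.025%

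*Protocol*

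**What the plan says.** Protocol 11.13 treats BP Fiasp versus Control as a separate study with its own testing hierarchy, and Fiasp SAP section 8 gives that hierarchy an initial alpha of 0.05. Its sample basis is stated as "This analysis will include approximately 100 participants in BP Fiasp and 50 participants in" Control. Fiasp SAP section 5 agrees: "RCT completion is expected for 100 adults randomized to the BP Fiasp" group, and 50 to Control.

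The protocol's two power statements are "HbA1c: Statistical power is 91%, assuming true mean HbA1c difference of 0.4% between BP" Fiasp and Control, and "Time <54 mg/dL: Statistical power is 86%, assuming no true difference in mean time <54 mg/dL". The Fiasp SAP repeats both, the first as "HbA1c: Statistical power is 91%, assuming true mean HbA1c difference of 0.4% between" the two groups.

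The listed assumptions are:

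- **HbA1c (superiority):** difference 0.4, SD 0.8, baseline correlation 0.40, two-sided type 1 error 5%.
- **Time <54 mg/dL (non-inferiority):** true difference 0, margin 1, SD 2.0, baseline correlation 0.40, one-sided type 1 error printed as 0.025%.

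The Endpoints row of the Protocol Summary sets the non-inferiority criterion at a one-sided p below 0.025. Protocol 11.6.2 and SAP 9.2 explain that this has the same rejection region as the corresponding half of a two-sided 0.05 test.

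The planned randomised adult numbers are larger than the completer numbers: "the BP Fiasp Group, or the Control Group (~110, 110, and 55 participants, respectively". On how the powers were derived, the Fiasp SAP says only "A separate document details the justification of these power calculations"; section 5 of the main SAP says the same.

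**The concern.** After dividing each effect by its SD, the two endpoints present the same power problem: same effect size, correlation, sample and critical value. Two different answers, five points apart, cannot both follow from those inputs, and rounding does not explain a gap of that size.

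These are the power statements for a comparison with its own alpha, in analyses intended to support a PMA submission. A reader should be able to reproduce them from the stated assumptions and cannot. On the printed basis the primary-endpoint figure errs in the favourable direction.

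The printed alpha is a second, independent slip. Read literally, 0.025% is 0.00025, one hundred times stricter than the test the plan describes. It appears in all four time <54 mg/dL power statements: Protocol 11.3 and 11.13, SAP section 5 and Fiasp SAP section 5.

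**Working it through.** **Inputs** (Protocol 11.13; Fiasp SAP 5)

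- Standardised effect for HbA1c: 0.4 / 0.8 = 0.50.
- Standardised effect for time <54 mg/dL: (1 − 0) / 2.0 = 0.50.
- Correlation ρ = 0.40 for both, so the residual SD factor after baseline adjustment is √(1 − 0.40²) = √0.84 = 0.9165.
- n = 100 versus 50.
- Critical value 1.96 for both, reading the non-inferiority alpha as 0.025.

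**Formula**

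SE (in SD units) = √(1 − ρ²) × √(1/n₁ + 1/n₂); ncp = 0.50 / SE; power = Φ(ncp − 1.96). The t version uses the noncentral t distribution with n₁ + n₂ − 3 degrees of freedom.

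**Check on the main comparison** (200 versus 100, ρ = 0.40)

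SE = 0.9165 × √0.015 = 0.1122; ncp = 4.454; power = Φ(2.494) = 99.4% (t 99.3%). This is consistent with the >99% and 99% stated in Protocol 11.3 and SAP 5, so those figures are not questioned.

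**Fiasp versus Control as printed** (100 versus 50, ρ = 0.40)

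SE = 0.9165 × √0.03 = 0.1587; ncp = 3.150; power = Φ(1.190) = 88.3% (t 87.9%) for both endpoints.

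- Against 91%: the stated figure is 2.7 points (normal) or 3.1 points (t) too high.
- Against 86%: the stated figure is 2.3 points (normal) or 1.9 points (t) too low.

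**Search for an origin of the stated figures** (effect 0.50 SD, one-sided 0.025 unless noted)

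| n | Variance assumption | Power (normal) | Power (t) |
|---|---|---|---|
| 100 / 50 | ρ = 0.40 | 88.3% | 87.9% |
| 100 / 50 | correlation ignored | 82.3% | 81.8% |
| 100 / 50 | change score, ρ = 0.40 | 75.0% | 74.5% |
| 100 / 50 | ρ = 0.40, one-sided 0.05 | 93.4% | – |
| 110 / 55 | ρ = 0.40 | 91.0% | 90.7% |
| 110 / 55 | correlation ignored | 85.7% | 85.3% |
| 93.5 / 46.75 (assumed 15% loss from 110 / 55) | ρ = 0.40 | 86.1% | 85.6% |

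No single row gives both 91% and 86%. Solving for the correlation at 100 versus 50, 91% needs ρ = 0.485 (t 0.495) and 86% needs ρ = 0.314 (t 0.332). The stated pair could therefore have come from the randomised numbers with baseline adjustment for one endpoint and none for the other, or from completer numbers with a different correlation for each endpoint. Neither can be confirmed from the documents.

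**The alpha as printed**

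At one-sided 0.00025 the critical value is 3.481.

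- Fiasp: Φ(3.150 − 3.481) = 37.0%, against 86% stated.
- Main comparison: Φ(4.454 − 3.481) = 83.5%, against 99% stated.

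The literal reading is incompatible with the plan's own powers as well as with its decision rule, so it is a units slip.

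**The case against.** The strongest reply has four parts.

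1. **The raw inputs are not literally identical.** They match only after standardising and after reading 0.025% as 0.025. That is true, but the standardising is plain division and the plan's own decision rule fixes the alpha. The literal alpha would move the stated 86% much further from reproducible.
2. **The HbA1c figure reproduces at the randomised numbers.** The ITT analysis includes all randomised participants, and 110 versus 55 with ρ = 0.40 gives 91.0%. This stands as a plausible origin for that one figure. It is not the sample stated in the paragraph, however, and the same 110 versus 55 with ρ = 0.40 also gives 91% for time <54 mg/dL, so it cannot explain 86%.
3. **A different method may lie behind the 86%.** Time <54 mg/dL has a rank-based fallback if skewed. With an assumed rank-test efficiency of 0.955, 100 versus 50 gives 86.8% (normal) or 86.4% (t). This is an illustration only: the printed inputs are means and SDs, and no rank-based power calculation is mentioned.
4. **The main-comparison check does not settle which sample size was used.** At 220 versus 110, ρ = 0.40 gives 99.7% and ρ = 0 gives 99.0%, which also fits >99% and 99%. This is correct. The check shows that the formula is compatible with the plan's other figures; it does not identify the source of the error.

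It is also fair to say that the consequence is modest. The protocol states that "The sample size of 440 for the RCT was selected to provide sufficient exposure to the iLet BP" system for regulatory purposes, and the Fiasp SAP was written after enrolment had finished, so planning power can no longer alter the design.

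**Conclusion.** The concern holds. One standardised calculation is printed with two answers, and the printed inputs give neither: about 88% for both endpoints, against 91% and 86%. This assumes a baseline-adjusted comparison of means, 100 versus 50 participants, ρ = 0.40 and one-sided 0.025. That the two powers must be equal needs less: only that one method was used for both endpoints.

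Which printed item is wrong cannot be determined without the separate power document. If the intended sample was 110 versus 55 with ρ = 0.40, the HbA1c figure is right, the sample statement is wrong, and the time <54 mg/dL figure should also be 91%.

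The type 1 error of 0.025% is a misprint for 0.025. The errors make the power statements irreproducible but do not undermine the design: with ρ = 0.40, power is 88% to 91% for both endpoints at either sample size.

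**What to change.** Check Protocol 11.13 and Fiasp SAP section 5 against the separate power document, then make the correction that matches it:

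- If 100 versus 50 and ρ = 0.40 were intended, restate both powers as 88%.
- If 110 versus 55 and ρ = 0.40 were intended, state those numbers as the basis and give 91% for both.
- If the two endpoints used different correlations, samples or methods, print them separately so that each power can be reproduced.

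In Protocol 11.3 and 11.13, SAP section 5 and Fiasp SAP section 5, print the one-sided type 1 error as 0.025 (2.5%).

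The cost is a text correction. Sample size, tests, margin and decision rules stay as they are.
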